## 9.6 Analyses

### 9.6.1 Accrual Period 1 PK and Safety Interim Analyses

Interim PK and safety analyses will be conducted when the first 10-12 accrual period 1 participants per treatment arm have completed 28 days of ART and day  $12 \pm 2$  (after initiation of ART) drug concentrations are available. These early assessments will try to identify any early trends suggesting lower or higher than expected concentrations of any study-provided drug(s). If early assessments indicate concentrations out of acceptable ranges for more than three participants in a treatment arm or trends related to safety criteria, an early ACTG Study Monitoring Committee (SMC) evaluation will be triggered.

The accrual period 1 PK and safety interim analysis will be conducted when 54-60 accrual period 1 participants have completed 28 days of ART and day  $12 \pm 2$  (after initiation of ART) PK results are available. Study participants who discontinue study follow-up prior to day 28 will have their safety data included in the safety analysis. Furthermore, study participants who are lost-to-follow-up prior to day 28 will be considered failures in the safety analysis. Because these participants will be undergoing treatment for active TB, they will continue on their randomized therapy pending the results of this interim PK and safety analysis, but accrual will be suspended until the final accrual period 1 PK and safety interim analysis has been reviewed by the SMC.

For RBT (Arms A and C), an equivalence approach will be used to compare day  $12 \pm 2$  (after initiation of ART) RBT 24-hour AUC and  $C_{max}$  with control data derived from prior PK studies, as determined by whether the 90% CI of the ratios of the RBT concentrations (when co-administered with LPV/r) relative to daily RBT concentrations in the absence of LPV/r are fully contained within the pre-specified NEB of 67%-150%. RBT concentrations in Arms A and C will be judged acceptable if equivalence is declared according to these PK parameters. (Please note: the control data derived from prior PK studies are described in section 10.3.)

For LPV (Arm B), the primary PK parameter is the  $C_{min}$  (trough or 12-hour post dose concentration), and the acceptable lower limit value is  $\geq 1$  mg/L. LPV/r concentrations in Arm B will be judged acceptable if no more than three participants have a  $C_{min} < 1$  mg/L.

For all treatment arms, the safety endpoint is all  $\geq$  Grade 3 AEs attributable to study-provided drug(s) by 28 days after ART initiation and all discontinuations of

study-provided drug(s) for treatment-limiting toxicity or intolerance (such that PK assessments within the days  $12 \pm 2$  (after initiation of ART) window cannot be completed). The arms will be judged to pass the safety criteria if no more than three participants have reported  $\geq$  Grade 3 AEs attributable to study-provided drug(s) by 28 days after ART initiation and if no more than 3 participants discontinued study-provided drug(s) for treatment-limiting toxicity or intolerance (such that PK assessments could not be completed).

#### 9.6.2 Analysis of the Primary Objective

All participants enrolled into A5290 will be included in the analysis of all the overall study objectives regardless of any required dose adjustments for accrual period 1 participants. The protocol team discussed the effect of including participants enrolled during accrual period 1 who underwent dose adjustments in the final analysis of the primary endpoint. The protocol team acknowledges that it is possible that those enrolled during accrual period 1 who had low LPV concentrations and required a dose adjustment might have worse HIV viral load responses at week 48, or alternatively, those who underwent a dose adjustment of one or more study-provided drugs might have greater toxicity that could adversely affect adherence, early treatment discontinuation, and HIV viral load responses at week 48. There remains significant uncertainty around what the major drivers will be of the week 48 virologic outcomes in this setting, such that including all participants in an intent-to-treat analysis accounting for all factors that might have contributed to the endpoint, including low levels requiring dose adjustment, higher toxicity leading to non-adherence or dose interruptions, prolonged intensive TB treatment phase, etc. will be a part of the study analysis plan. The protocol team also acknowledges that it is possible that those enrolled during the accrual period 1 could be different than those enrolled during the accrual period 2. Besides seeking as homogeneous a population as possible, baseline tables of factors that could affect drug concentrations (e.g., sex, prior ART experience, body weight, etc.) will be summarized by accrual period.

The primary outcome variable will be the rates of virologic suppression at 48 weeks within each treatment arm. Participants lost-to-follow-up or without virologic data will be considered failures (i.e., not suppressed). The rate in the double-dose LPV/r arm will be separately compared to the standard dose LPV/r arms in two analyses. The rates between the two arms will be compared using an asymptotic normal binomial test (Arm A versus Arm B; Arm C versus Arm B).

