Confirmed extrapulmonary TB is defined as the presence of compatible clinical symptoms as previously described plus clinical features of organs involved, such as sterile pyuria or other renal involvement, pericarditis, ascites, pleural effusion, meningitis, arthritis, orchitis, enteritis, extrathoracic lymphadenitis, or osteitis and positive culture for MTB or nucleic acid amplification test positive for MTB or MTB Complex from fluid or tissue biopsies from any of these organ or tissue sites, including bone marrow, liver, and blood.

Probable Pulmonary TB is based on the clinician's judgment and includes compatible clinical symptoms as previously described, and at least one of the following: 1) positive sputum smear for acid fast bacilli (AFB); or 2) abnormal CXR, chest CT scan or other chest imaging; or 3) evidence of granulomata with organisms positive for AFB or caseating granulomata on lung tissue biopsy; or 4) positive tuberculin skin test (TST) ( $\geq$  5mm) or interferon gamma release assay (IGRA); and without concurrent illness that would explain the findings, but MTB cultures are negative or not available.

Probable Extrapulmonary TB is based on the clinician's judgment and includes compatible clinical symptoms as previously described plus clinical features of organs involved as previously described, or evidence of granulomata with organisms positive for AFB or caseating granulomata on tissue biopsy from relevant site(s); and specific antituberculous therapy initiated or recommended, but MTB cultures are negative or not available.

NOTE: Participants whose qualifying episode of TB was later determined not to be TB will continue to be followed on study but off study drugs for safety and ART endpoints.

- 4.1.4 Chest x-ray within 30 days prior to study entry.
- 4.1.5 A PI-based ART regimen is required, as determined by the participant's primary clinician/clinical facility.

NOTE: Enter the reason, in the eligibility checklist, for the PI-based ART regimen from among the following choices:

The PI-based therapy was required:

- 1) Because the participant failed an NNRTI regimen or;
- 2) Because the participant had an adverse reaction to an NNRTI regimen or;
- 3) Because the participant received single dose nevirapine during pregnancy and could have NNRTI resistance mutations archived at the time the participant was starting ART;
- 4) Other, specify.

4.1.6 Laboratory values obtained within 14 days prior to study entry:

Accrual period 1

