### 9.3 Randomization and Stratification

The participants will be randomized 1:1:1 to three open-label arms using permuted blocks. Randomization will not be stratified.

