Because the primary objective entails comparing virologic efficacy of Arm A versus Arm B and Arm C versus Arm A, we will have two hypothesis tests and will use an alpha-level of 0.025 for each test (thus, overall alpha-level = 0.05). If we assume the overall virologic efficacy of the double-dose LPV/r arm is 50%, and the standard LPV/r dosed arm coupled with RBT is 70% by 48 weeks (and 80-90% for LPV/r and RAL with RBT-based anti-TB treatment), 147 participants per arm will provide 90% power to detect a 20% difference in virologic response rates by 48 weeks between the double-dose LPV/r arm and the standard LPV/r plus RBT arm and adequate power for the comparison of the standard LPV/r plus RBT arm and adequate power for the comparison of the standard LPV/r plus RBT plus RAL arm compared to both other treatment arms. This assumes using a two-sample, two-sided 0.025-level asymptotically-normal binomial test.

Participants lost to follow-up will be considered as failures. Participants determined to have RIF-resistant TB isolates after enrollment will be taken off study, referred to their local clinician or clinical facility to receive best available local standard of care, and will not be replaced. Assuming that 3% of participants will have RIF resistance at entry and be taken off study, we will need to adjust the sample size to require 152 participants per arm. Adjusting the sample size again by 3% for interim analyses requires 157 participants per arm. Based on these data and assumptions, the estimated overall sample size will be 471 participants.

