## **3 Baseline Characteristics**

- Table of age, sex, race, and ethnicity by treatment arm.
- Table of Karnofsky performance score and body mass index (BMI) by treatment arm.
- Table of CD4 count and HIV RNA ( $\log_{10}$  copy number and number below lower limit of quantification).
- Table of reason PI-based therapy was needed from eligibility checklist [Q0017-Q0018] (category and specific reason if category=other) by treatment arm.
- Table of AFB smear and mycobacterial culture results by treatment arm.
- Table of RIF and INH drug susceptibility testing (DST) results by treatment arm.
- Table summarizing days from randomization to TB treatment initiation, days from randomization to study-provided ARV treatment initiation, and days from TB treatment initiation to ARV treatment initiation by treatment arm.

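### The week-48 primary test is valid and adequately powered as planned, but in an unstratified trial it leaves unused the baseline HIV RNA, CD4 and reason for PI therapy that the trial already collects

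*Protocol*

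**What the plan says.** **Primary test.** Protocol 9.6.2 defines the outcome as suppression at week 48, counts participants without data as not suppressed, and says the rates "will be compared using an asymptotic normal binomial test (Arm A versus Arm B; Arm C versus Arm B"). It names no baseline covariate and no adjusted sensitivity analysis.

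**Randomisation.** Protocol 9.3 uses permuted blocks, 1:1:1, and adds: "Randomization will not be stratified".

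**Sizing.** Protocol 9.4.2 states that "147 participants per arm will provide 90% power to detect a 20% difference in virologic response rates by 48 weeks", that the team "will use an alpha-level of 0.025 for each test (thus, overall alpha-level = 0.05"), and that "This assumes using a two-sample, two-sided 0.025-level asymptotically-normal binomial test". Design and analysis therefore use the same unadjusted test.

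**Baseline data in hand.** Protocol 4.1.2 requires a CD4 count before entry, and 6.3.10 requires a screening HIV RNA. On the reason for PI therapy, 4.1.5 instructs sites: "Enter the reason, in the eligibility checklist, for the PI-based ART regimen from among the following choices". The choices are NNRTI failure, NNRTI adverse reaction, single-dose nevirapine in pregnancy, and other. SAP section 3 lists a "Table of CD4 count and HIV RNA" and a table of the reason for PI therapy by arm. Neither feeds a model.

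**Nearest wording to adjustment.** Protocol 9.6.2 speaks in general terms of an intent-to-treat analysis that takes contributing factors into account. Its examples (low drug levels, toxicity, interrupted dosing, prolonged intensive TB treatment) all arise after randomisation, and no model is given. Protocol 9.6.3 lists logistic regression, but for secondary and additional analyses and without covariates.

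**The concern.** In an unstratified trial, covariates that predict outcome add noise to an unadjusted comparison. A baseline-adjusted risk difference estimates the same quantity with smaller variance when those covariates are prognostic, and it accounts for imbalance in the sample actually drawn.

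The protocol gives its own reason to expect prognostic value. Section 2.1 describes substantial NRTI resistance after failure of an NNRTI regimen and the resulting risk of virologic failure, and 9.4.2 relies on similar reasoning for its expected rates. Yet 4.1.5 admits participants with and without such failure.

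At stake are some precision and the credibility of the week-48 comparison if the arms differ visibly at baseline. There is a second cost to saying nothing: the loose wording on contributing factors could be read as licence to adjust for post-randomisation variables, which could bias an intent-to-treat contrast.

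**Working it through.** **1. The plan's own figure.** Inputs from protocol 9.4.2: 50% (Arm B), 70% (Arm A), two-sided 0.025, 90% power.

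n = [z(0.9875)·√(2·p̄·q̄) + z(0.90)·√(p0·q0 + p1·q1)]² / d²

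- p̄ = 0.60, so √(2 × 0.60 × 0.40) = √0.48 = 0.6928
- √(0.25 + 0.21) = √0.46 = 0.6782
- (2.2414 × 0.6928 + 1.2816 × 0.6782)² / 0.20² = 2.4221² / 0.04 = 146.7, so 147 per arm; power at 147 is 90.07%
- 147/0.97 rounds up to 152; 152/0.97 rounds up to 157; 3 × 157 = 471

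The stated design reproduces exactly.

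**2. Gain from adjustment at 147 per arm.** Assumption: the baseline covariates explain a share R² of the outcome variance. The documents give no value. Effective n = 147/(1 − R²); the n per arm for equal power is 147 × (1 − R²), rounded up.

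| R² (assumed) | Effective n | Power, 50% v 70% | Equivalent n per arm | Power, 50% v 65% |
|---|---|---|---|---|
| 0 | 147.0 | 90.1% | 147 | 64.2% |
| 5% | 154.7 | 91.6% | 140 | 66.7% |
| 10% | 163.3 | 93.0% | 133 | 69.4% |
| 15% | 172.9 | 94.4% | 125 | 72.1% |
| 20% | 183.8 | 95.6% | 118 | 75.0% |

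**3. Simulation check, 147 per arm, 4,000 trials per scenario.** Unadjusted test against a risk difference standardised from a logistic model with three baseline covariates, for 50% versus 70%:

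- R² 0: 90.9% v 90.5%
- R² 0.05: 91.1% v 92.7%
- R² 0.12: 89.5% v 92.9%
- R² 0.24: 90.5% v 96.5%

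Under the null the unadjusted test rejected 2.2–2.5% of the time and the adjusted one 2.5–3.1%, against a nominal 2.5%. The simulation standard error is √(0.025 × 0.975/4,000), about 0.25 points, so the excess is small, but it all points one way.

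**4. Parsimonious version.** An adjusted risk difference with two baseline covariates and HC3 variance gave type I error of 2.1–2.5% at both 147 and 20 per arm. At 147 per arm, power went from about 90% to 93% (R² 0.11) or 95% (R² 0.24), with a loss of about 1 point at R² 0. At 20 per arm there was no gain.

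**5. The size that exists.** SAP 1.6 says accrual period 2 will not open; accrual period 1 is 20 per arm. Power of the planned test at 50% versus 70% is Φ[(0.20 − 2.2414 × √(0.48/20)) / √(0.46/20)] = Φ[(0.20 − 0.3472)/0.1517] = Φ(−0.97), about 17%.

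**6. Chance imbalance.** For a factor with 50% prevalence, the between-arm difference has SD √(2 × 0.25/n). At 147 per arm this is 5.8 points (95% range ±11.4); at 20 per arm it is 15.8 points (±31).

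**The case against.** The case against is strong on several counts, and most of it stands.

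- **The planned test is correct.** A reader might infer that leaving out the covariates biases the comparison or inflates its error rate. It does neither. Randomisation balances baseline factors in expectation, the test's type I error already covers chance imbalance, and the simulated rate stayed at or below 2.5%.
- **The trial is not underpowered by design.** A reader might infer a power shortfall. On the protocol's own assumptions the unadjusted test reaches 90%.
- **Prognostic strength is unknown.** Protocol 9.6.2 itself admits uncertainty about what will drive week-48 outcomes. Counting missing data as failure could also weaken any link with baseline HIV RNA or CD4.
- **The gain at 147 per arm will not be realised** if accrual period 2 stays closed.
- **A careless adjustment can do harm.** In simulation at 20 per arm, a logistic model with log10 HIV RNA, CD4 and a four-level reason (frequencies assumed to be 60/20/10/10%) failed to fit in 42–51% of trials. Where it fitted, it rejected a true null 6.1–6.6% of the time, against 1.9–2.6% for the planned test.
- **The SAP's silence is not a defect.** By its stated purpose it covers only the PK and safety interim report.

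These points limit the claim and shape the fix. They do not remove it: no section specifies a baseline-adjusted analysis of the primary endpoint, and a small model with a suitable variance avoids the instability.

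**Conclusion.** The point holds as an inexpensive improvement in efficiency and credibility. It does not correct bias or type I error. At the designed size and effect, adjustment would add about 1.5 to 5.5 points of power if the covariates explain 5–20% of outcome variance, which is an assumption. If they explain nothing it would add nothing or cost about 1 point. The gain is larger for a smaller true effect: at 50% versus 65% and an assumed R-squared of 10%, 64.2% becomes 69.4%.

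The documents do not support presenting this as a gain the trial will now obtain. At about 20 per arm, power is near 17% and adjustment cannot rescue it. What remains at that size is a prespecified answer to baseline imbalance, which can then be large. That still has value, because protocol 9.6.2 keeps all enrolled participants in the overall analyses and is the only specification of the week-48 comparison in the documents supplied.

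**What to change.** Amend protocol 9.6.2; the supplied SAP is not the place, since it does not cover the week-48 analysis.

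1. Prespecify a baseline-adjusted risk difference for A versus B and C versus B, each at the existing 0.025 level. Covariates: log10 HIV RNA, CD4 count, and reason for PI therapy collapsed to NNRTI failure yes/no.
2. Use a small-sample robust variance, for example HC3 with a t reference distribution.
3. State that only pre-randomisation variables enter the model, and that drug levels, toxicity, dose changes and treatment duration do not.
4. Keep the unadjusted test as a sensitivity analysis.
5. If enrolment stays at about 20 per arm, use at most one or two covariates and report the adjusted estimate as supportive, beside the unadjusted test.
6. Fix the covariates before any by-arm week-48 result is examined.

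Section 9.4.2 names the second primary contrast as C versus A, whereas 9.6.2 names C versus B. Reconcile these in the same edit.

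**Cost:** protocol text and a few lines of code, with no new data or visits. The downside is a slightly more complex analysis and a small loss of power if the covariates turn out not to be prognostic.

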#### 9.6.3 Analysis of the Secondary Objectives

Secondary objectives and additional analyses will be evaluated with statistical techniques appropriate to the data type and specific question, including but not limited to Wilcoxon tests and logistic regression for dichotomous endpoints and Cox proportional hazards regression for time-to-event endpoints. Some analyses will consider change between baseline and target time points, such as weeks 24 and 48. Continuous variables may be dichotomized based on conventional cut points (e.g., median or CD4  $<50$ ). Except for select analyses of virologic

suppression that are reviewed by the DSMB, the alpha-level for these exploratory and hypothesis-generating analyses will not be adjusted for multiple testing.

## 10.0 PHARMACOLOGY PLAN

### 10.1 Pharmacology Objectives

- 10.1.1 To evaluate LPV PK characteristics (AUC,  $C_{\max}$ ,  $C_{\min}$ ) in study participants enrolled in Arms A, B, and C, accrual periods 1 and 2.
- 10.1.2 To evaluate the RBT PK characteristics (AUC,  $C_{\max}$ ,  $C_{\min}$ ) in study participants enrolled in Arms A and C, accrual periods 1 and 2.
- 10.1.3 To evaluate the RAL PK characteristics (AUC,  $C_{\max}$ ,  $C_{\min}$ ) in study participants enrolled in Arm C, accrual period 2.

### 10.2 Pharmacology Study Design for the Dose-Finding Study in Accrual Period 1 Participants

A5290 is a prospective evaluation in participants undergoing treatment for confirmed or probable TB and who require PI-based ART. The dose-finding study in accrual period 1 participants of A5290 is designed to evaluate two primary questions: 1) Is a RBT dose of 150 mg once daily when given with LPV/r adequate? and 2) Is an LPV/r dose of 800/200 mg BID when given with RIF adequate? Intensive PK evaluations will be performed on day  $12 \pm 2$  (after initiation of ART) of concomitant TB and HIV therapy on all accrual period 1 participants.

#### 10.2.1 Sample Size

The sample size for the dose-finding study in accrual period 1 participants will be 20 participants per treatment arm, randomized 1:1:1 for a total of 60 participants.

#### 10.2.2 Sampling Strategy

Arms A and C, RBT pharmacokinetics. Plasma samples will be obtained just prior (pre-dose) and for 24 hours after administration of the morning dose of RBT at the following times: 2, 4, 5, 6, and 24 hours (next day) after the dose. Plasma will be frozen and batch shipped every 2 weeks to the ACTG repository, which will immediately re-ship them to the designated ACTG Pharmacology Support Laboratory (PSL). Refer to the A5290 LPC for additional instructions.

Arms A, B, and C LPV pharmacokinetics. Plasma samples will be obtained just prior to administration of the morning dose of LPV/r, and at the following times: 2, 4, 5, and 6 hours after the dose. A pre-dose concentration will be taken to be a 12-hour post dose concentration. Plasma will be frozen and batch shipped every 2 weeks to the ACTG repository, which will immediately re-ship them to the designated PSL. Refer to the A5290 LPC for additional instructions.

This sampling strategy requires that the once daily dose of RBT be taken with the morning dose of LPV/RTV for Arms A and C, and that the morning dose of RAL for Arm C be taken with the morning dose of LPV/RTV.

#### 10.2.3 Medication Adherence

All participants should be counseled to ensure strict compliance with their TB and HIV medications. Participants should be queried as to the number of doses of TB and HIV medications not taken in the previous 3 days, and this number should be recorded on the CRF. The time and date of all doses of all TB and HIV medications taken the day prior to the PK study day (i.e., day  $12 \pm 2$  of concomitant therapy) must be recorded on the CRF. The time of all doses of TB and HIV medications given on the day of the PK study should be recorded on the CRF. The PK study should not be performed if participants report missing any doses of any TB or HIV medication on the day prior to the PK study. If this situation occurs, the participant should be counseled about medication adherence, and a repeat PK study may be performed  $\geq 5$  days later, and no more than 12 days later than the originally scheduled PK study. If on this second PK day, the same participant should report missing any doses on the day prior to the PK study, the PK study should not be performed and this individual will not be considered eligible for the PK study.

A measured LPV pre-dose (or 12-hour post dose concentration) that is below the limit of quantitation (BLQ,  $< 20$  ng/mL) will be taken as objective evidence for non-adherence. Any participant in Arm B of the accrual period 1 with a LPV C12 that is BLQ will not be considered for assessment of the accrual period 1 LPV PK passing criterion. Similarly, a measured RBT pre-dose concentration that is BLQ will be taken as objective evidence of non-adherence for participants in Arms A and C of the accrual period 1. Any participant with a RBT pre-dose concentration that is BLQ will not be included in evaluation of the accrual period 1 RBT PK passing criterion evaluation. Any participants determined to have clearly inadequate RBT concentrations during accrual period 1 evaluation should be monitored closely for TB outcomes throughout the course of their TB treatment.

